**Secondary Variables**

LN detection rate with PINPOINT or Blue dye, defined as the proportion of cases in which at least one LN is identified with PINPOINT or Blue dye (confirmed as lymphoid tissue by histology).

Incidence of adverse events and adverse device events/effects of PINPOINT and Blue dye.

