## **9 EVALUATION, RECORDING, AND REPORTING OF ADVERSE EVENTS**

All untoward medical occurrences either observed by the Investigator or one of his/her medical collaborators, or reported by the subject spontaneously, or in response to the direct question below, will be reported as follows:

- All events occurring before randomization should be recorded in the source documents and will be considered part of the subject's case history.
- All adverse events occurring during the study will be recorded as adverse events on the adverse event CRF.
- Events occurring as a result of the surgery will be reported as adverse events related to the surgical procedure in the adverse event CRF.
- Events related to PINPOINT will be recorded as adverse device effects in the CRF.
  - Events that are not related to PINPOINT shall be recorded as adverse events.
- Events related to PINPOINT that affect a user of the device (non-subject) are recorded as technical complaints.
- Events related to IC2000 and/or Blue dye will be recorded as adverse events related to IC2000 and/or blue dye in the adverse event CRF.

In an attempt to optimize consistency of AE reporting across centers, the subjects must be asked a standard question to elicit events. At each clinic or telephone evaluation of the subject, study personnel will ask the following questions: "Have you had any problems since your last visit?"

AEs reported on the CRF will include the date of onset, severity, relationship to PINPOINT, IC2000 and/or Blue dye, relationship to surgical procedure, date of resolution (or the fact that it is ongoing or has become chronic), action taken, and whether the AE is serious or not.

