### 9.1.2 Adverse Device Effect (ADE)

Any adverse event related to the use of PINPOINT (includes all hardware components).

- Includes any event that is a result of a use error or intentional misuse.

ADEs that affect subjects will be recorded as ADEs in the AE CRF. ADEs that only affect a user (non-subject) are recorded in the technical complaint form only.

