### 10.6.2 Safety Variables and Analysis

Safety variables will be documented and summarized for all randomized subjects enrolled in the study who received at least one injection of IC2000 or Blue dye. Safety variables will include all adverse events (AEs) and adverse device effects (ADEs), concomitant medications, and vital signs. Safety analysis will be performed on all subjects who receive IC2000 regardless of whether LN mapping was initiated or successful.

Adverse events will be coded using the National Cancer Institute Common Terminology Criteria for Adverse Events (NCI CTCAE). Treatment-emergent AEs and ADEs will be summarized descriptively. The number and percentage of subjects experiencing AEs and ADEs and the total number of AEs and ADEs will be summarized by system organ class and preferred term. Associated AEs that investigators suspect are related to study treatment will also be summarized. Summary of each type of event will be prepared by severity and for all severities combined.

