Safety Outcomes

One secondary objective of the study is to assess the safety of interstitial injection of IC2000 for intraoperative lymphatic mapping. Tables 9, 10, and 11 summarize the data to address this secondary objective. These analyses will be performed on the safety (S) analysis set. Adverse events include Adverse Device Effects.

Table 9. Summary of Adverse Events				
Concise Term	Intensity	Relationship to Study Drug / Surgery	Number of Adverse Events	
			B-P Arm	P-B Arm
Term #1	Mild	Not Suspected		
	Moderate	Not Suspected		
	Severe	Not Suspected		
	Mild	Related to Blue Dye		
	Moderate	Related to Blue Dye		
	Severe	Related to Blue Dye		
	Mild	Related to Fluorescent Dye		
	Moderate	Related to Fluorescent Dye		
	Severe	Related to Fluorescent Dye		
	Mild	Related to Surgery		
	Moderate	Related to Surgery		
	Severe	Related to Surgery		
Term #2	Mild	Not Suspected		
	Moderate	Not Suspected		
	Severe	Not Suspected		
	Mild	Related to Blue Dye		
	Moderate	Related to Blue Dye		
	Severe	Related to Blue Dye		
	Mild	Related to Fluorescent Dye		
	Moderate	Related to Fluorescent Dye		
	Severe	Related to Fluorescent Dye		
	Mild	Related to Surgery		
	Moderate	Related to Surgery		
	Severe	Related to Surgery		
Etc.				
Total				

We will use Fisher’s exact test to compare study arms with respect to the distribution of intensity and relationship to study drug/surgery for each adverse event. We will estimate the incidence of each adverse event with a 95% exact binomial confidence interval.

Maximum Intensity	B-P Arm		P-B Arm		Total	
	N	%	N	%	N	%
Mild						
Moderate						
Severe						
Total						

We will use Fisher’s exact test to compare the distribution of maximum intensity of adverse events between study arms. We will estimate the percent of subjects with each maximum intensity level with a 95% exact binomial confidence interval.

We will provide a listing of all adverse events by study arm and subject, as shown in Table 11.

Arm	Subject	Concise Term	Intensity	Date of Onset	Date Resolved	Action Taken	Relationship to Study Drug / Surgery	Outcome

Protocol Deviations

We will list all protocol deviations for patients screened and enrolled on the study.

Arm	Subject	Date	Deviation	Other ...	Description	Severity

Other Data Summaries

We will provide listings of conditions, illnesses, or surgical procedures from the subjects' baseline medical history by subject and study arm (Table 13).

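### SAP safety tables have no PINPOINT-related category, so no SAP output gives the adverse device effect incidence that the protocol names as a secondary variable

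*SAP*

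**What the plan says.** **Protocol.** Secondary Variables in the Protocol Summary names "Incidence of adverse events and adverse device events/effects of PINPOINT and Blue dye". Section 9.1.2 ties an ADE to use of the PINPOINT system, including its hardware. Section 9 records dye-related events separately from ADEs, and requires the CRF to capture "relationship to PINPOINT, IC2000 and/or Blue dye, relationship to surgical procedure". Section 10.6.2 commits to a subject-level summary: "The number and percentage of subjects experiencing AEs and ADEs and the total number of AEs and ADEs will be summarized". The breakdown there is by organ class and by coded term.

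**SAP, Safety Outcomes.** The text states "Adverse events include Adverse Device Effects". Table 9 classifies each event under "Relationship to Study Drug / Surgery" with four levels (not suspected, Blue dye, fluorescent dye, surgery), and its only data columns are numbers of events in each arm. Table 11, the listing, carries the same relationship column. Fisher's exact test is to be used "to compare study arms with respect to the distribution of intensity and relationship to study drug/surgery for each adverse event". The SAP then plans an exact binomial interval for the incidence of each adverse event, without stating the unit of the numerator or the denominator. A further table gives N and % by maximum intensity, with exact intervals for the percentage of subjects at each level.

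**The concern.** The protocol treats the device, IC2000, Blue dye and surgery as four possible causes. The SAP tables keep three of them and drop the device, in a study whose Protocol Summary describes it as a pivotal investigational device study. An analyst who programs the shells literally must either place a device-related event in a row that does not describe it or leave it out of the relationship breakdown. Either way, the SAP outputs would not contain a variable that the protocol names.

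Two smaller matters sit in the same table. Event counts do not give the subject-level figure that the protocol promises. A Fisher test on those counts treats several events in one subject as independent observations. Because both arms receive both dyes, the test also compares order of injection and mapping, and a reader could mistake a non-significant result for evidence of safety.

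**Working it through.** The plan states no figure to reproduce here. The check sets the protocol against the SAP outputs, with some arithmetic on what the missing output would show.

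**1. Where could a PINPOINT-related event go in Table 9?**

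- *Not suspected:* no. Protocol Section 9.2.2 keeps this for events whose link to the study device or treatment can reasonably be ruled out.
- *Fluorescent dye:* no. That is IC2000, which Section 9 records separately from PINPOINT.
- *Blue dye* or *surgery:* no. Each is a different cause.

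**2. Does another SAP output separate ADEs?**

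- *Table 11 (listing):* same drug-or-surgery column, so not as headed.
- *Maximum-intensity table:* counts subjects, but has no relationship or ADE breakdown.
- *Incidence sentence under Table 9:* by adverse event term, not by cause.

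None does.

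**3. Is the information collected?** Yes. Under Section 9, relationship to PINPOINT is a CRF item and device-related events are recorded as ADEs.

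**4. What would the missing output show?** The SAP plans about 150 evaluable subjects but does not fix the size of the safety set, so 150 is assumed. With no events, the upper end of a two-sided exact 95% interval is 1 − 0.025^(1/n).

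| Subjects with an ADE | Incidence | Exact 95% interval |
|---|---|---|
| 0 of 150 | 0% | 0 to 2.4% |
| 1 of 150 | 0.7% | 0.02 to 3.7% |
| 2 of 150 | 1.3% | 0.2 to 4.7% |
| 3 of 150 | 2.0% | 0.4 to 5.7% |

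With 138 subjects (150 less the 8% the plan expects to have mapping aborted, 150 × 0.92), zero events give an upper limit of 1 − 0.025^(1/138) = 2.6%. A one-sided 95% limit for 0 of 150 would be 1 − 0.05^(1/150) = 2.0%, so the report should say which is meant.

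**5. Can incidence be recovered from Table 9's event counts?** No. As an assumed example, six events of one term among 150 subjects could come from one subject (1/150 = 0.7%, interval 0.02 to 3.7%) or from six (6/150 = 4.0%, interval 1.5 to 8.5%).

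**6. What does an arm comparison measure?** B-P and P-B subjects both receive both dyes and both mappings, so only order differs. Take a simple with-or-without-event Fisher test on subjects, 75 per arm, with the same true rate in both arms. The exact probability of p ≤ 0.05 is:

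| True rate in both arms | Probability of p ≤ 0.05 |
|---|---|
| 1% | 0.0001 |
| 2% | 0.002 |
| 5% | 0.015 |
| 10% | 0.027 |
| 20% | 0.031 |

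It stays below 0.05 however common the harm. The test is silent on the absolute rate unless order matters.

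**The case against.** The strongest reply is that nothing is lost. Protocol Section 10.6.2 remains in force and promises subject-level AE and ADE counts. The SAP does not withdraw that promise, calls its tables mock-ups, and expressly brings ADEs into the analysis. This largely stands. A reader might infer that the trial would report no device-related incidence at all; the documents do not support that. What remains is that the SAP, the document that specifies the outputs, does not carry out the commitment.

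Other strong readings also fail:

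- **The safety section counts only events.** This is true of Table 9's cells only. The maximum-intensity table counts subjects and has exact intervals.
- **The incidence intervals will be computed on event counts.** The SAP does not say so. An exact binomial interval presupposes subjects, and the protocol specifies subjects. The fair criticism is that the unit is not stated.
- **The arm tests prevent an incidence estimate, or are offered as tests of IC2000 or device safety.** They do neither. The SAP says only that arms are compared, and comparing randomized sequences is a legitimate check for order effects. Dropping the tests would be a preference.
- **The safety objective is unmet.** That objective concerns interstitial ICG, and Table 9 has fluorescent-dye rows by intensity. The gap concerns the named ADE variable.

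**Conclusion.** The point holds in a limited form. As the SAP shells stand, a PINPOINT-related event has no correct row in Table 9 and no matching category in the Table 11 column. No SAP output gives the ADE incidence that the protocol names and promises per subject. This rests on the row and column labels, which are legible and repeat identically for both example terms in Table 9. It is a failure to implement a protocol commitment; data collection is not at fault.

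In size, the missing output is one line per category, for example 0 of 150 subjects with an interval of 0 to 2.4%. The 150 is assumed, and 138 would move the upper limit to 2.6%. These figures show what should be reported; they do not measure an error in the plan. The event-level Fisher test is a secondary weakness confined to Table 9.

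**What to change.** - Add a level for events related to the PINPOINT device to Table 9, and extend the relationship column of Table 11 to include the device.
- Add a table of subjects with at least one event (n, %) on the pooled safety set, for all events and separately for IC2000-related, Blue-dye-related and device-related events. Keep event counts beside it, as Section 10.6.2 asks for both.
- State that incidence and its exact binomial intervals are per subject, two-sided 95%, and name the denominator.
- If the Fisher tests are kept, run them on subjects and label them as comparisons of injection and mapping order.

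The cost is minor table-shell and wording work, with the matching programming. Relationship to PINPOINT is already on the CRF, so no new data or change in conduct is needed.
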